Women randomized to GnRH_{AG}+exercise will come to the Exercise Research Laboratory (ERL) for a supervised exercise program. The exercise facility in the ERL is open for research participants 6:30-8:30am, 11:30am-1:30pm, and 4:30-6:30pm Mon through Fri. The goal of the exercise program will be to generate an increase in EE of ~1400 kcal/wk to offset the projected decrease in PAEE. Women will be instructed to come in at least 3 days per week so that regular oversight and encouragement for exercise can be provided. The center-based program will be augmented with recommendations for home-based exercise to meet the weekly exercise goals. Individualized, endurance-based (e.g., treadmill, elliptical, rowing, cycling) exercise prescriptions will be designed to increase energy expenditure by 200-300 kcal per session. As an example, a 75-kg woman with a maximal aerobic power (VO₂max) of 25 mL/min/kg exercising at 65% of VO₂max would have to exercise ~40 min to increase energy expenditure by ~200 kcal. Exercise duration and intensity will be modified according to individual preferences to enhance compliance.

2.d.8. Compliance

All participants must come to the Clinical and Translational Research Center (CTRC) every 4 weeks for 24 weeks for GnRH_{AG} and placebo injections. Compliance to the drug intervention will be tracked by the research nurse, who will deliver all of the injections. If the delivery of a dose is delayed (e.g., participant misses an appointment), it will be administered as soon as possible.

Compliance to center-based exercise will be monitored directly by the staff of the ERL that supervises exercise sessions. Participants will be contacted by the research staff when 3 consecutive sessions are unexpectedly missed. Exercise logs will be used to record the activities performed at the ERL; this information will be computerized so that the supervised exercise exposure can be calculated. Home-based exercise will be captured for all participants through the measurements of TEE by DLW and physical activity by accelerometry.

2.d.9. Tests and procedures

2.d.9.1. Baseline testing schedule and methods

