Visit 2 – TEE by DLW and body composition by DXA. This visit will initiate the measurement of TEE by DLW. The pre-intervention 10-d test will start during the mid-follicular phase of the menstrual cycle. Participants will report to the lab in the morning after an overnight fast. A urine specimen will be collected and the participant will then consume an oral dose of water containing 1.8 g/kg total body water (TBW) of 10 atom percent excess (APE) ¹⁸O and 0.12 g/kg TBW of 99.9 APE ²H following procedures developed by [name].⁷⁴ Urine samples for the measurement of ²H₂¹⁸O will be obtained approximately 3 and 4 hours after dosing. Two urine samples will also be collected 10 days after dosing, 1 hour apart. Sample aliquots of 4 mL each will be stored in cryogenic tubes and frozen at -10C. Samples will be decolorized with 200 mg/5 mL of dry carbon black and filtered (0.45 micron). The stable isotope abundances will be measured by isotope ratio mass spectrometry and TEE will be calculated as previously described.⁷⁵⁻⁷⁷ The **rationale** for the DLW procedure is that it is the most accurate and precise measure of TEE under free-living conditions.^{78,79} The major advantages of the DLW method are its objectivity, minimal interference with daily activities, accuracy, and precision. It is objective because the body water acts as a metabolic recorder; the participant does not have to keep logs or report a history. The tracer elimination rates are determined from spot urines collected on the day the tracer is given by mouth and again at the end of the period, so there is little disruption of daily activities. The DLW method has a coefficient of variance of ±1%.⁸⁰

Body composition by DXA. Body composition will be measured by DXA (Hologic Discovery). The lumbar spine and proximal femur scans will not be repeated at this visit; baseline values will be obtained at screening. The operation of the DXA instrument in the PI's lab includes daily measurements of the spine phantom, weekly air scans, and tissue bar scans at least once per month. The reproducibility of measurements has

Figure 9. Baseline testing schedule (W = week; V = visit); weeks 0 and -4 correspond roughly with the start of menstrual cycles

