been assessed in 40 women and men, aged 23-86 y, measured on 3 occasions over 1 mo. The coefficients of variation (CV) for total mass, FFM, and fat mass were $0.8\pm 0.8\%$, $0.8\pm 0.8\%$, and $2.3\pm 2.7\%$, respectively. The CVs for BMD of the lumbar spine, total hip, femoral neck, and trochanter were $1.3\pm 0.7\%$, $1.1\pm 0.9\%$, $1.9\pm 1.0\%$, and $1.4\pm 1.0\%$, respectively. Total body scans will be analyzed for total fat mass and FFM, and regional (i.e., legs, arms, and trunk) fat mass. An increase in the ratio of trunk-to-leg fat mass in response to GnRH_{AG} will be interpreted as a shift in fat distribution pattern toward increased abdominal adiposity.^{9,10}

At visit 2 participants will also return the ActivPal and be given nutrition handouts instructing them on how to prepare for their OGTT by maintaining a diet that includes at least 150g/day of carbohydrates.

Visit 4 – urine sample for DLW, chamber stay, OGTT, tissue biopsies, OPTIONAL Vascular Sub-study. These tests may be conducted over 2 visits if scheduling does not permit the chamber stay to occur on day 10 of the DLW interval.

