Chamber stay. Participants will report to the CTRC at 0700h after an overnight fast. A urine sample for DLW will be obtained, if necessary. An IV catheter will be positioned in an antecubital vein and a fasted blood sample will be obtained. Participants will enter the chamber at 0800h. A reclining chair will be positioned next to the port in the chamber through which blood samples are obtained. Participants will rest for the first hour. At 0900h, they will drink a 75-g glucose beverage and remain semi-recumbent for the next 2 hours for the TEF measurement. To mimic typical activity outside the calorimeter, two 30-min bouts of treadmill walking at 3 mph will be performed at 1500h and 1630h. This activity should produce a physical activity level (PAL; TEE/REE) of ~1.5 (unpublished observations, [name] and [name]). All urine will be collected and analyzed for urine nitrogen, urea nitrogen, and creatinine for substrate oxidation calculations. Core temperature will be measured during the chamber stay using an ingestible thermistor capsule (length 23 mm, diameter 8.6 mm) and a VitalSense telemetric monitor. TEE will be calculated as previously described.⁵³ Stepping EE will be measured during the exercise bout. SEE will be measured from 0100h to 0400h.⁸¹ Pre-study diet and exercise are known to affect 24-h fat oxidation.^{82,83} Subjects will be asked to refrain from structured exercise the day before the chamber stay. Diet will not be controlled because of the possibility that energy intake (and possibly macronutrient preference) is influenced by ovarian function. The energy composition of the diet for the chamber stay will be 30% fat, 55% carbohydrate, and 15% protein, with the 75g glucose beverage accounting for breakfast and about 25% of total energy needs, while both lunch and dinner will each account for about 30-35% of total energy needs. 'Extra' calories will be provided in the form of a snack box that participants will have free access to from the time the lunch meal is delivered until lights out. Participants will be instructed to eat what they want and that it is not necessary to eat all the food provided. This approach may provide insight on whether the suppression of ovarian function promotes hyperphagia. Data from each calorimeter stay will be evaluated for state of energy balance.

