The **rationale** for the chamber stay is to **1)** obtain a prolonged measure of basal metabolic rate for the calculation of PAEE, **2)** obtain a measure of TEE under controlled conditions, **3)** determine whether TEF is influenced by GnRH_{AG}, and **4)** determine whether EE during a specific physical task (stepping activity) is influenced by GnRH_{AG}. PAEE will be the difference between TEE measured by DLW (adjusted -10% for TEF) and SEE measured during the chamber stay, as previously described.¹⁴ The OGTT will be performed in the calorimeter to avoid a separate visit for participants and to assess whether the TEF is influenced by GnRH_{AG}.⁸⁴

Blood samples during the chamber stay. Blood samples will be obtained before and 30, 60, 90 and 120 min after glucose ingestion. These will be used for the measurement of insulin resistance (product of the glucose and insulin areas under the curve) and inflammatory cytokines (IL-6, hsCRP) for **SA3**. The assays will be performed by the CTRC core laboratories. The extent to which changes in disease risk could be explored was limited by the resources available under the P50 mechanism. Measures of insulin resistance and mild chronic inflammation were selected because of the prominent role these factors play in metabolic dysfunction.⁸⁵

Chamber stay alternative. Heavy use of the metabolic chamber for multiple research protocols has created scheduling difficulties. Subjects who cannot complete the 24-hr metabolic chamber stay in a timely manner will be offered the option of completing this alternative approach. Subjects will report fasted to the CTRC at 7:00am and will have vitals measured and an IV catheter inserted for the OGTT. At 7:30am they will consume a 75-g glucose beverage and remain semi-recumbent for the next 3 hours for the OGTT and TEF measurements. Blood samples will be drawn before and 30, 60, 90 and 120 min after glucose ingestion. The IV will be removed after the last blood sample. TEF will be measured through indirect calorimetry using the ventilated

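### The exercise-free day before the chamber stay falls, by default, inside the 10-day DLW window, which can modestly understate TEE and PAEE in the exercise arm (SA4)

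*Combined protocol and SAP*

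**What the plan says.** The relevant statements are in different parts of the protocol.

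- **Restriction (2.d.9.1, Chamber stay).** "Subjects will be asked to refrain from structured exercise the day before the chamber stay". The sentence before it gives 24-hour fat oxidation as the reason; PAEE is not mentioned.
- **DLW window (2.d.9.1, Visit 2).** The dose is taken in the morning after a fast. The window closes as follows: "Two urine samples will also be collected 10 days after dosing, 1 hour apart".
- **Timing of the stay (2.d.9.1, Visit 4).** The tests may be split over two visits "if scheduling does not permit the chamber stay to occur on day 10 of the DLW interval", so day 10 is the default. Women arrive at 0700h, give a DLW urine sample if one is needed, and enter the chamber at 0800h.
- **Derivation of the outcome (2.d.9.1).** "PAEE will be the difference between TEE measured by DLW (adjusted -10% for TEF) and SEE measured during the chamber stay".
- **Exercise arm (2.d.7).** "The goal of the exercise program will be to generate an increase in EE of ~1400 kcal/wk". Sessions are "designed to increase energy expenditure by 200-300 kcal per session". On attendance: "Women will be instructed to come in at least 3 days per week", with home exercise added to reach the weekly goal.
- **Repetition (2.d.9.2).** Visits 1 to 4 are repeated in weeks 10-12 and 22-24.
- **Chamber alternative (2.d.9.1).** The ventilated-hood option states no exercise restriction.

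No section mentions the overlap, says whether a session due that day should be moved, or plans an adjustment.

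**The concern.** DLW was chosen because it records free-living expenditure with little interference. A protocol instruction not to exercise on one of the ten recorded days is interference, and it serves a different endpoint.

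The instruction applies to every woman at every chamber visit, but its effect is not equal across arms. Programmed exercise exists in one arm only and starts after baseline. A programmed session omitted on the restricted day therefore lowers the change score in that arm and in no other. SA4 asks whether exercise offsets a fall in PAEE, and section 2.d.7 leaves open that exercise may bring no net gain. The error runs in that direction. H4 also names TEE, which is affected directly.

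Exposure is uneven as well. If the stay moves off day 10, the restricted day can leave the window, and the hood alternative has no such day. The same section describes heavy demand on the chamber, so a mix of the three situations is plausible both across women and across one woman's visits. The plan does not ask for this to be recorded.

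**Working it through.** **1. Sequence.** A morning dose on day 0 and closing urine on the morning of day 10 give a 10-day window. A stay that starts on the morning of day 10 makes day 9 to day 10 the restricted period. It lies wholly inside the window, as 1 day of 10.

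**2. The plan's own power figure (2.d.4).** Inputs: SD 330 kcal, correlation 0.90, difference 200 kcal/d, 15 per group, alpha 0.05 (sidedness not stated; two-sided assumed).
- SD of change = sqrt(2 x (1 - 0.90)) x 330 = 147.6, stated as 148.
- Standard error of a two-group difference = 148 x sqrt(2/15) = 54.0. Noncentrality = 200/54.0 = 3.70.
- Noncentral t power is 94.6% with 28 df and 95.1% with 42 df (three-group error). The stated 95% is reproduced.

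**3. Energy lost if a session is omitted and not made up (inputs from 2.d.7).**
- Sessions per week to reach the goal: 1400/300 = 4.7 to 1400/200 = 7.
- Average at full adherence: 1400/7 = 200 kcal on any one day; 200/10 = 20 kcal/d of 10-day mean TEE, for either session size.
- Maximum, for a woman due a 300-kcal session that day: 300/10 = 30 kcal/d.
- Three sessions a week: 3 x 200/7/10 = 8.6 to 3 x 300/7/10 = 12.9, so about 9-13 kcal/d on average.
- Session moved to another day of the interval: 0.

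**4. Conversion to PAEE.** Under 0.9 x TEE minus SEE, 20 becomes 18 and 30 becomes 27 kcal/d. Against 200 kcal/d, that is 18/200 = 9% to 27/200 = 13.5%. Section 2.d.2 instead subtracts a measured TEF; if TEF is unchanged by the missed session, the full 20 to 30 kcal/d carries over. The power table therefore covers 18 to 30.

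**5. Power for GnRH agonist versus GnRH agonist plus exercise** (SD 148, two-sided 0.05, three-group error df: 42 at 15 per group, 63 at 22):

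| Dilution (kcal/d) | Difference seen | 15 per group | 22 per group |
|---|---|---|---|
| 0 | 200 | 95.1% | 99.3% |
| 18 | 182 | 90.8% | 98.0% |
| 20 | 180 | 90.2% | 97.8% |
| 27 | 173 | 87.8% | 96.8% |
| 30 | 170 | 86.7% | 96.3% |

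The 22 column assumes that every enrolled woman is analyzed.

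**6. Added variance from uneven exposure.** If half the exercise arm lost 30 kcal/d and half lost nothing, the added SD is 15, and sqrt(148² + 15²) = 148.8. This is negligible; the shift in the mean is what matters.

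**The case against.** A reader might infer that the plan removes exercise from its own primary measurement. It does not. The restriction covers structured exercise on one day in ten, and 170 to 182 of a 200 kcal/d difference would still be seen. Dilution of that size cannot by itself produce a finding of no net gain.

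A reader might also infer that the primary contrast is biased. The documents do not support this. Neither the placebo nor the GnRH agonist arm has programmed exercise, and the outcome is change from a baseline measured under the same instruction. Section 3.1.a also excludes women who exercise at moderate to vigorous intensity for at least 30 minutes on more than 4 days a week. What may remain is a slight under-recording of voluntary exercise in both arms.

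The best argument against acting is that the exercise goal is weekly and flexible. At 300 kcal per session a woman has about 7 - 4.7 = 2.3 rest days a week, and the restricted day can be one of them. Nothing in the chamber text waives the weekly goal. This stands in part: the loss may well be zero for many women. But the plan does not tell women or staff to move the session. Nor would its records reliably show what happened. Section 2.d.8 specifies logs for center sessions only, and the activity monitor issued at Visit 1 comes back at Visit 2, when the DLW window opens.

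It is also fair that day-10 stays cannot be assumed for everyone, given the chamber bottleneck. That lowers the average loss, but it is also the source of the uneven exposure.

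**Conclusion.** The overlap is real and nothing in the plan corrects it. Its consequence is confined mainly to SA4: TEE and PAEE in the exercise arm at weeks 12 and 24 can be understated, and the contrast shifts modestly toward no effect. At the weekly target without make-up, the average loss is about 20 kcal/d of TEE (18 of PAEE) and the maximum is 30 (27). Power with 15 per group falls to about 91-87%. With 22 per group it stays at 96% or more, though a larger sample does not remove a directional error. Severity is minor.

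The figures assume that the stay is on day 10, that adherence equals the target except where three sessions a week is stated, that exercise energy adds fully to TEE, that the omitted session is 200-300 kcal, and that a 200 kcal/d difference would otherwise be seen. The order of visits is taken from the text, since Figure 9 was not available to me.

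**What to change.** 1. Time the DLW dose so that both closing urine samples are collected before the exercise-restricted day begins, for example with the dose at least 11 days before the stay and the restriction starting once the samples are taken. The fat-oxidation safeguard is kept, and Visit 4 may already be spread over two visits.
2. Use the same order at baseline, weeks 10-12 and weeks 22-24.
3. Where this cannot be arranged, state that the weekly exercise goal still applies and that a session due on the restricted day is moved to another day of the interval.
4. For each DLW interval, record the chamber date (or use of the hood alternative) and whether a restricted day fell inside the window. Use this in a sensitivity analysis of SA4 under the robustness step in 2.d.10.

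Cost: one scheduling sentence and one data field. The test block becomes up to one day longer, which matters most at baseline, where testing is meant to finish within one menstrual cycle. There is one short extra urine drop-off, or a home collection that is unsupervised.

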Other secondary outcomes of the study will include: 24-h TEE measured by DLW; REE, SEE, and TEF measured by indirect calorimetry in a metabolic chamber; energy intake estimated from food records; physical activity measured by accelerometry; body composition measured by dual-energy x-ray absorptiometry (DXA); glucose and insulin responses to an OGTT; serum concentrations of inflammatory cytokines (IL-6, hsCRP); and biomarkers in adipose tissue samples.

2.d.3. Study population

Volunteers will be women nearing the menopausal transition, based on age (40 to 60 y), with normal menstrual cycle function. The **rationale** for this approach was driven by the observation that a menopause-related decline in PA likely begins 3 to 4 years before menopause (Fig 6). We chose not to focus the study on women with perimenopausal symptoms for two reasons: 1) we may miss part of the perimenopause-related change in PAEE, and 2) the irregularity of menstrual cycles during the perimenopause complicates the scheduling of baseline tests around menstrual cycle phase. Specific inclusion and exclusion criteria are in Section 3.1.a.

2.d.4. Sample size justification

The expected effect of ovarian hormone suppression on PAEE was conservatively set at -25%, based on the range of decreases in physical activity observed in preclinical studies of -30% to -80% (Fig 1) and the decrease

of -50% in the prospective cohort study of women undergoing natural menopause.¹² Baseline PAEE was assumed to be 800 kcal with a SD of 330 kcal.⁶⁵ The variance of the difference between PAEE_{pre} and PAEE_{post} is $2(1-\rho)\sigma^2$. Using a conservative value of 0.90 for ρ (actual value, 0.98)⁶² and assuming no change in variance as PAEE decreases, the SD of the change will be 148 kcal/d. Based on the analysis plan to conduct a 1-way ANOVA with two contrasts (placebo vs GnRH_{AG}; GnRH_{AG} vs GnRH_{AG}+exercise), a sample size of 15 in each of 3 groups will achieve 95% power for either test to detect a 200 kcal/d difference between two groups in the change in PAEE using a *t* test at the 0.05 significance level. To account for attrition, we will enroll 22 per group.

2.d.5. Screening procedures

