Figure 9 depicts the baseline testing schedule. Given the intensive nature of the testing, some flexibility will be necessary to accommodate the schedules of the participants. However, the general plan is to initiate visit 1 during the early follicular phase of the menstrual cycle so that all testing can be completed before the end of the cycle. This will facilitate starting the GnRH_{AG} intervention in the early part of the next menstrual cycle.

Visit 1- RMR, EI, PA, VO₂max. This visit will occur in the early follicular phase. Participants will report to the lab at approximately 0700h after an overnight fast.

Resting metabolic rate (RMR). After lying quietly for 30 min, RMR will be measured for 15-20 min by indirect calorimetry using the ventilated hood method (Parvo Medics metabolic cart) as previously described.³⁷ RMR will be used to estimate the energy needed to maintain energy balance.

[figure not shown]
Measurement of physical activity. Physical activity will be measured using ActivPal monitors. The ActivPal categorizes free-living activity into periods spent sitting/lying, standing, and walking. This information can be used to estimate daily energy expenditure and track changes in free-living activity profile. There is no display to provide feedback to the participant. Participants will be instructed to wear the monitor for 7 consecutive days at all times except when sleeping or participating in water-based activities (e.g. showering, swimming). Activity and step counts will be summed over the day and further analyzed to calculate the minutes per days spent in resting, ambulation, or lifestyle activities using a two-regression model.⁷³ The **rationale** for assessing PA by accelerometry is to compare the changes with those observed in women as they approach the natural menopause.¹²

VO₂max. VO₂max will be measured by indirect calorimetry during treadmill exercise as previously described.⁵⁸ The **rationale** for this test is that it will guide the prescription of exercise intensity for the GnRH+exercise group and will reveal whether decreases in PAEE are accompanied by a decrease in cardiovascular fitness.

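### The 75-g glucose drink cannot supply about 25% of chamber-day energy needs, so the food provided falls below the stated shares and snack intake alone cannot be read as hyperphagia

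*Combined protocol and SAP*

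**What the plan says.** Section 2.d.9.1, Visit 4, Chamber stay, makes the glucose drink both the oral glucose challenge and the whole breakfast: "At 0900h, they will drink a 75-g glucose beverage and remain semi-recumbent for the next 2 hours for the TEF measurement". The diet is then apportioned "with the 75g glucose beverage accounting for breakfast and about 25% of total energy needs". The other two meals are also set as percentages: "while both lunch and dinner will each account for about 30-35% of total energy needs". A snack box of additional food is freely available from lunch until lights out, and participants may eat as much or as little as they wish. Of this arrangement the plan says: "This approach may provide insight on whether the suppression of ovarian function promotes hyperphagia". The paragraph ends by stating that each chamber stay will be evaluated for energy balance.

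Three other statements bear on the arithmetic:

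- On the treadmill bouts in the chamber: "This activity should produce a physical activity level (PAL; TEE/REE) of ~1.5".
- On how needs are set (section 2.d.9.1, Visit 1): "RMR will be used to estimate the energy needed to maintain energy balance".
- On the primary outcome (section 2.d.4): "Baseline PAEE was assumed to be 800 kcal with a SD of 330 kcal". The chamber rationale in section 2.d.9.1 defines PAEE as DLW-measured TEE reduced by 10%, minus SEE.

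No expected RMR, SEE or TEE is given.

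**The concern.** The energy in 75 g of glucose is fixed and small. Calling it a quarter of daily needs implies needs far below what the plan's other figures allow. The error sits in the operative feeding rule, not in background text. If the kitchen works from it, women are given less on the chamber day than the protocol states.

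Two things are at stake. First, the snack box is presented as surplus food whose consumption might reveal overeating. If breakfast is under-provided, part of what is eaten from the box only makes up the missing energy. Because the drink is fixed while the meals scale with needs, that part is larger for women with higher needs. Second, one stated purpose of the chamber stay is to measure TEE under controlled conditions, and the intended energy provision is part of that control.

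**Working it through.** **Inputs.** Drink 75 g; stated share 25%; lunch plus dinner 60-70%; PAL 1.5 (all from Chamber stay). PAEE 800 kcal (section 2.d.4). PAEE = 0.9 × TEE − SEE (chamber rationale). Assumptions not in the documents: 4 kcal/g for glucose, and the resting expenditure (REE) values below.

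**1. Needs at which 25% would be true.** 75 × 4 = 300 kcal, and 300 / 0.25 = 1,200 kcal/d. A lower energy value widens the mismatch: at 3.4 kcal/g the drink is 255 kcal and needs would be 1,020 kcal/d.

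**2. Check against the plan's PAL.** REE = 1,200 / 1.5 = 800 kcal/d (680 at 3.4 kcal/g).

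**3. Check against the plan's PAEE.** With free-living TEE of 1,200, SEE = 0.9 × 1,200 − 800 = 280 kcal/d. This uses free-living rather than chamber expenditure, so it is a plausibility check only. It points the same way.

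**4. A rough anchor for REE.** The exercise example in section 2.d.7 (75 kg, 25 mL/min/kg, 65%, 40 min, about 200 kcal increase) gives 75 × 25 × 0.65 / 1,000 = 1.219 L/min. At an assumed 4.8-5.0 kcal/L the gross cost over 40 min is 234-244 kcal. Subtracting 200 and scaling to 24 h gives resting expenditure of about 1,220-1,575 kcal/d. This is sensitive to rounding of the 200 kcal, but it lies within the range used below.

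**5. The plan's stated provision.** 25% + 60% to 25% + 70% = 85-95%, so 5-15% is left to the snack box by design.

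**6. Recomputed provision.** Needs = 1.5 × REE; drink share = 300 / needs; left before snacks = needs × (30% to 40%) − 300; part due to the drink = 0.25 × needs − 300.

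| Assumed REE (kcal/d) | Chamber needs (kcal/d) | Drink share | Drink + meals | Left before snacks (kcal) | Part due to the drink |
|---|---|---|---|---|---|
| 1,100 | 1,650 | 18.2% | 78.2-88.2% | 195-360 | 6.8 points, 112.5 kcal |
| 1,333 | 2,000 | 15.0% | 75-85% | 300-500 | 10.0 points, 200 kcal |
| 1,500 | 2,250 | 13.3% | 73.3-83.3% | 375-600 | 11.7 points, 262.5 kcal |
| 1,667 | 2,500 | 12.0% | 72-82% | 450-700 | 13.0 points, 325 kcal |

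At an REE of 2,000 the share would be 10%. No value from 1,100 to 2,000 brings it near 25%.

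**7. Could the gap differ by arm?** Section 2.c reports REE falls of 42 and 71 kcal/d under short-term ovarian suppression. If falls of that size occurred here, needs would drop by 63-106.5 kcal/d. The amount left before snacks would change by 30-40% of that, about 19-43 kcal.

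**The case against.** A reader might infer that the snack-box comparison is confounded. The documents do not support this. The same drink and meal rules apply in every arm, and section 2.d.9.2 repeats the same visits at weeks 10-12 and 22-24. A common shortfall does not bias a randomised comparison of change, and step 7 shows that any difference between arms arising through REE is small. If appetite, and so energy balance, differs by arm, that follows from the deliberate free-access design and not from the 25% figure.

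A reader might also infer that the whole pre-snack gap is due to the drink, or that women end the day in deficit. Neither follows. The plan's own shares leave 5-15% uncovered, and the snack box is open for the rest of the day.

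A third inference is that the primary PAEE is affected through SEE. TEE in PAEE comes from DLW. The documents give no size for any effect of one day's intake on overnight SEE, and women using the chamber alternative have RMR in its place. This link is not shown.

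Finally, the stakes are low. The hyperphagia remark is tentative, the listed energy-intake outcome in section 2.d.2 comes from food records, and section 2.d.10 includes no snack-box analysis. The plan also already undertakes to evaluate energy balance for each stay. These points stand and limit the severity. They do not rescue the 25% figure or make snack calories interpretable on their own.

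**Conclusion.** The 25% is wrong as written. On the assumed REE range of 1,100-1,667 kcal/d and 4 kcal/g, it overstates the drink's share by a factor of about 1.4 to 2.1 (25/18.2 to 25/12). The mismatch itself needs only the energy value of glucose and the plan's own PAL and PAEE; its exact size depends on the assumed REE.

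Two consequences hold: the stated energy provision for the chamber day is not met, and absolute snack intake cannot by itself be taken as evidence of hyperphagia. Bias in the between-arm comparison of change, or in the primary outcome, is not established. Severity is minor.

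**What to change.** - Replace the 25% with the share that 75 g of glucose supplies for each woman, calculated from her RMR-based estimate of needs.
- State the intended total provision before snacks, and reconcile the lunch and dinner shares with it.
- Express chamber intake (drink, meals and snacks together) relative to estimated needs, rather than as snack calories alone.
- Report the already planned energy-balance evaluation by arm, and say in section 2.d.10 how it will be used.

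The cost is a corrected figure, a change to the meal calculation and one or two lines in the analysis plan. No extra visits or measurements are needed. If stays have already been completed under the current rule, the last two items can still be done, provided the food eaten was recorded.
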